#### **Objective 1:**

To evaluate the primary outcome by intervention arm, we will use a linear mixed model to conduct an analysis of covariance (ANCOVA), controlling for site type (ED vs. Urgent Care), index visit pain severity, age, gender, race, medical comorbidities (as the Gagne score), baseline intermittent opioid use, a history of chronic pain, and access to a PCP. These control variables were selected *a priori* based on prior evidence of prognostic value and will not be subjected to significance testing. This model will include all BPI-SF average scores (1, 3, and 6) as outcomes, will include fixed effects for group, time, and group-by-time, as well as all of the control variables, and will use an unstructured covariance matrix for the error terms. We will specify a 6 degrees of freedom (df) linear contrast to test the overall null hypothesis of no mean difference in BPI-SF score at any follow-up visit across the 3 groups at the 5% significance level. If the overall null hypothesis is rejected, we will then conduct separate 3 df contrasts to compare each of the intervention groups with the control group using a Bonferroni-adjusted 2.5% significance level. We will estimate mean pairwise differences along with 95% confidence intervals at each time point. Missing BPI-SF data will be ignored for the primary comparison. The primary analysis will be conducted using the ITT Population, but will also be repeated using the PP Population.

We will also conduct a sensitivity analysis of the primary comparisons using a multiple imputation approach. Pain scores for patients taking analgesics in the past week will be imputed using demographic characteristics, history of chronic pain, pain location, pain etiology (traumatic vs. not traumatic), baseline pain severity, analgesics used, and treatment group.

We will use similar ANCOVA models to test the intervention effects on the secondary outcomes. For continuous or ordinal outcomes, we will use generalized estimating equations models and contrast tests. For any binary variables (e.g., opioid use or non-use) we will also use ANCOVA model but will fit mixed-effect logistic regression models.

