**Figure X****Figure Y****Figure Z**

Thus, we created an exemplary dataset in which participants in the full intervention and video-only groups experienced post-randomization mean pain scores of 20% or 15%, respectively, lower than that in the usual care group. We assumed that loss-to-follow-up times would be exponentially distributed such that the total loss would be 20% at 12 months. Under these assumptions, randomizing 120 participants to each group would provide at least 90% power for testing the overall null hypothesis of no difference across the three groups in mean change from baseline to any follow-up visit through the 6-month visit using linear contrast tested at the 5% significance level (Figure Z).

Furthermore, this sample size would provide about 93% power for the comparison between the full intervention and the usual care group and 67% power for the comparison between the video-only group and the usual care group under these same assumptions, each tested at Bonferroni-adjusted 2.5% significance levels. Because we would like our sample size to support both the intention to treat analysis and the per protocol analysis (restricted to non-admitted patients) and assuming that up to 10% of enrolled patients will be admitted, we plan to enroll 400 patients. The sample size is not calculated based on secondary outcomes. In order to avoid selective reporting of secondary outcomes, we will register and report all secondary outcomes regardless of what is found. The MIXED Procedure in SAS, version 9.4 (SAS Institute, Cary, NC) was used for calculations.

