The Gagne Comorbidity Score will be calculated based on baseline data. The weights indicated below will be applied to each item, as detailed here: <https://scholar.harvard.edu/gagne/software/combined-comorbidity-score> .

```

if disease = 'metastatic_romano' then weight = 5;
if disease = 'chf_romano' then weight = 2;
if disease = 'dementia_romano' then weight = 2;
if disease = 'renal_elixhauser' then weight = 2;
if disease = 'wtloss_elixhauser' then weight = 2;
if disease = 'hemiplegia_romano' then weight = 1;
if disease = 'alcohol_elixhauser' then weight = 1;
if disease = 'tumor_romano' then weight = 1;
if disease = 'arrhythmia_elixhauser' then weight = 1;
if disease = 'pulmonarydz_romano' then weight = 1;

```

```

if disease = 'coagulopathy_elixhauser' then weight = 1;
if disease = 'compdiabetes_elixhauser' then weight = 1;
if disease = 'anemia_elixhauser' then weight = 1;
if disease = 'electrolytes_elixhauser' then weight = 1;
if disease = 'liver_elixhauser' then weight = 1;
if disease = 'pvd_elixhauser' then weight = 1;
if disease = 'psychosis_elixhauser' then weight = 1;
if disease = 'pulmcirc_elixhauser' then weight = 1;
if disease = 'hivaids_romano' then weight = -1;
if disease = 'hypertension_elixhauser' then weight = -1;

```

6. Missing Outcome Data, Out of Window Visits, and Sensitivity Analyses

Missing data for the primary outcome will be ignored (treated as missing at random) in the primary ITT analysis. For the 1-, 3-, and 6-month visits, outcomes for any visits that fall outside the ± 7 day window will be set to missing for the primary analysis (with time computed as follow-up call date minus enrollment date). However, as a first sensitivity analysis, we will repeat the primary analysis using all observed data even if the visits fall outside the visit window. This analysis will repeat the same comparison of mean BPI-SF scores at 30, 90, and 180 days, but time will be treated continuously in this model and actual visit dates will be used. As a second sensitivity analysis, we will repeat the primary analysis using multiple imputation to account for any missing BPI-SF scores. The multivariate normal multiple imputation method will be used, and imputations will be based on all of the control variables included in the primary model.

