For each outcome measured using a scale, missing scale items will be imputed as described in Section 5 above. Data missing by design (e.g., due to a skip pattern in the data collection form) will be filled in logically where appropriate.

7. Analysis of Participant Follow-Up

We will present an account of the final disposition (completed, withdrew, lost, or died) for each participant in the ITT Population, including any admission violations and group assignment. The number and proportion of participants in the ITT population who provided information for the analyses of the study objectives will be summarized by randomization group. Frequencies of participants with missing primary outcome data will be summarized by randomization group and study visit. We will provide a CONSORT diagram showing the flow of participants through the trial, indicating withdrawals by treatment arm with reasons, when provided.

8. Analysis of Baseline Data

We will summarize baseline data (i.e., pre-randomization data) for the ITT Population, by randomization group, site type (ED vs. Urgent Care), and overall. Measures of central tendency and dispersion for continuous and certain discrete variables will include means, standard deviations, medians, minima, and maxima. Categorical data will be summarized with frequencies and percentages. Some continuous variables may also be grouped into categorical levels and evaluated in frequency tables. No inferential statistics (i.e., p-values and/or confidence intervals) for comparing data between groups will be presented.

9. Primary Analysis of Primary Outcome (Objective 1)

The primary analysis of BPI-SF will use the ITT Population, and will be repeated secondarily using the Per-Protocol Population. We will use a linear mixed model to conduct an analysis of covariance (ANCOVA), controlling for site type (ED vs. Urgent Care), baseline pain severity, age, gender, race,

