comorbidity score, baseline intermittent opioid use, a history of chronic pain, and access to a PCP (access to a PCP was used to stratify the randomization and, as such, it is important to control for it in all models). These control variables were selected a priori based on prior evidence of prognostic value and will not be subjected to significance testing. This model will include all pain severity scores (1, 3, 6, and 12 months) as outcomes; will include fixed effects for group, visit, and group-by-visit; and will use an unstructured covariance matrix for the error terms. We will first test a 6 degrees of freedom (df) linear contrast of the overall null hypothesis of no mean difference in the primary outcome at any of the 1-, 3-, and 6-month follow-up assessments across the 3 groups at the 5% significance level. If the overall null hypothesis is rejected, we will then conduct two separate 3 df contrasts to compare each of the intervention groups with the control group using a Bonferroni-adjusted 2.5% significance level. We will secondarily estimate mean pairwise differences along with 95% confidence intervals at each time point, including data collected at the 12-month follow-up time point.

10. Secondary and Exploratory Analyses (Objective 1)

The same linear mixed modeling approach used for the primary outcome will be applied to each of the separate components of the BPI-SF (Pain Severity and Interference). Similar comparisons using the sequence of linear contrasts and 95% confidence intervals as specified for the primary outcome will be made.

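### The imputation model in SAP section 6 leaves out randomized group, so this sensitivity analysis will generally understate a real group difference, though only slightly at the planned loss

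*SAP*

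**What the plan says.** The purpose of the second sensitivity analysis in SAP section 6 is plain: "we will repeat the primary analysis using multiple imputation to account for any missing BPI-SF scores". The method is multivariate normal, and "imputations will be based on all of the control variables included in the primary model".

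SAP section 9 shows which variables those are. The primary model is described as "controlling for site type (ED vs. Urgent Care), baseline pain severity, age, gender, race", continuing with "comorbidity score, baseline intermittent opioid use, a history of chronic pain, and access to a PCP". The section then calls these the control variables, chosen for prognostic value and not to be tested. Group comes in afterwards and separately: the model "will include fixed effects for group, visit, and group-by-visit".

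Protocol section 6.1 (Objective 1) also describes a multiple imputation, and its predictor list ends with "baseline pain severity, analgesics used, and treatment group". That imputation concerns pain scores of patients taking analgesics, and the SAP states in its introduction that it replaces the protocol's summary plan.

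The SAP does not say whether BPI-SF scores from other visits are used to impute a missing score.

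**The concern.** An imputation model should contain at least what the analysis model contains. Here the analysis model has group and group-by-visit, and the stated imputation predictors have neither. A participant with a missing score, whatever the arm, is then given a value typical of all three arms combined. When the completed data are used to compare arms, those values dilute a real difference. This happens even if scores are missing completely at random.

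What is at stake is how a check is read. The analysis is meant to show whether missing data matter. When an effect is real, it would differ from the primary result partly because of its own imputation model, and a reader could take the weaker estimate as a sign of fragility.

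**Working it through.** The documents give no figure for bias in this analysis, so there is none to reproduce. The starting point is the planned loss.

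**1. Missing share.** Protocol section 6.2 assumes that "loss-to-follow-up times would be exponentially distributed such that the total loss would be 20% at 12 months". Missing share at month t is 1 − 0.8^(t/12), which returns 20% at t = 12.
- 1 month: 1 − 0.8^(1/12) = 1.8%
- 3 months: 1 − 0.8^(3/12) = 5.4%
- 6 months: 1 − 0.8^(6/12) = 10.6%

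SAP section 6 also sets out-of-window scores to missing for the primary analysis. If these are imputed too, the shares rise. The expected amount is not given.

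**2. Control variables only, equal loss.** Assume loss unrelated to scores. Randomization balances covariates, so imputed values average the pooled observed mean M in every arm. The completed mean in arm a is (1 − m_a)·μ_a + m_a·M. With equal m, the difference between two arms is (1 − m)·Δ. Shrinkage is therefore m: 1.8%, 5.4% and 10.6%, whatever the between-visit correlation or time pattern.

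**3. Control variables only, unequal loss.** Now M = Σ(1 − m_a)μ_a / Σ(1 − m_a). Assume benefits of 0.5, 0.375 and 0 SD for full, video-only and usual care. The ratio follows the protocol's 20% and 15%; the 0.5 SD is my assumption.
- Missing 5/10/16%: M = 0.8125/2.69 = 0.302. Full minus usual care is 0.490 − 0.048 = 0.442 (shrinkage 11.6%). Video-only minus usual care is 0.368 − 0.048 = 0.319 (14.8%).
- Missing 16/10/5%: M = 0.7575/2.69 = 0.282. The shrinkages are 9.8% and 6.2%.

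**4. Other visits' scores also enter.** The protocol's correlations and usual-care means are in figures not available to me, so the correlation ρ is a range. Under planned dropout, the 10.6% missing at 6 months splits into 1.84% with no earlier score, 3.58% with month 1 only, and 5.13% with months 1 and 3. Without group in the model, the fitted variance includes the between-arm variance of the effects, v = variance of (0, 0.375, 0.5) = 0.045. For a constant effect, the part of the difference carried into the imputed values is:
- from one earlier visit, b1 = (ρ + v)/(1 + v)
- from two, b2 = 2(ρ + v)/(1 + ρ + 2v)

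Shrinkage = 0.0184 + 0.0358(1 − b1) + 0.0513(1 − b2).

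| ρ | b1 | b2 | Shrinkage at 6 months |
|---|---|---|---|
| 0.3 | 0.330 | 0.497 | 6.8% |
| 0.5 | 0.522 | 0.686 | 5.2% |
| 0.7 | 0.713 | 0.832 | 3.7% |
| 0.8 | 0.809 | 0.894 | 3.1% |

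The time pattern matters. For ρ from 0.5 to 0.7, and effect ratios at 1, 3 and 6 months of:
- 1.5:1.2:1 (declining): 3.1 to 1.2%
- 2:1.4:1 (steeply declining): 1.3 to −1.1%, a slight reversal
- 0.7:0.85:1 (growing): 6.5 to 5.4%

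A decline is possible because the protocol's planning effects are proportional to usual-care pain.

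**5. Simulation of proper multiple imputation** (133 per arm, one baseline covariate, constant effect, loss unrelated to scores). Covariate only: 10.8% and 10.5% shrinkage at 6 months for ρ = 0.5 and 0.7. Covariate plus visits: 7.1%, 6.0%, 4.1% and 3.4% for ρ = 0.3, 0.5, 0.7 and 0.8. With group and visits in the model, 6-month estimates were 0.495 to 0.506 against a true 0.5.

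**6. Size.** With a 6-month standard error of about 0.12 SD (√(2/133) = 0.123), the bias for a 0.5 SD effect is:
- control variables only, equal loss: 0.106 × 0.5 = 0.053 SD, or 0.44 standard errors
- other visits included, constant effect: 0.015 to 0.034 SD, or 0.13 to 0.28 standard errors

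**7. No true difference.** If loss is unrelated to scores, the bias is zero. Suppose instead that in one arm only, 6-month loss depends on the 3-month score (log-odds 0.3 to 1.0 per SD, ρ = 0.5, 10.6% missing in every arm). Imputation from control variables only then gives a false difference of about 0.015 to 0.04 SD.

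**The case against.** The best defence is that the sentence is under-specified rather than a decision to leave group out. It does not say that only the control variables will be used. The named method is a joint one that naturally takes the repeated scores together. The SAP also describes itself as expanding a protocol plan whose own imputation list names treatment group. This has some force as to intent. It does not cure the text: the protocol list belongs to a different imputation, the SAP supersedes it, and SAP section 9 keeps group apart from the control variables. A programmer following the SAP would have no instruction to include group.

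The defence is stronger on size. A reader might infer that the difference always shrinks by exactly the missing share. The documents do not support that, because it requires control variables only and equal loss by arm, and the SAP leaves the use of other visits open. A reader might also infer that nothing can go wrong when there is no true effect. That holds only if loss is unrelated to scores, whereas SAP section 6 treats missing data as missing at random, which allows loss to depend on earlier pain.

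It could be added that SAP section 7 lets a reader gauge the shrinkage, since "Frequencies of participants with missing primary outcome data will be summarized by randomization group and study visit". That works only under the same restrictive conditions.

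**Conclusion.** The omission is real and its consequence follows from the text: without group in the imputation model, a true difference is generally pulled toward zero. It is a minor point, confined to one of two sensitivity analyses.

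Under planned loss, equal across arms and unrelated to scores, the 6-month shrinkage is 10.6% with control variables only. It is about 3 to 7% if other visits enter with a constant effect, and near zero or slightly reversed if the effect declines steeply. Unequal loss moves the control-variables-only figure either way. The effect sizes and correlations are assumed, not taken from the documents.

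It would be wrong to read this as a flaw in the main result. The primary mixed model contains group and group-by-visit and does not use these imputations.

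**What to change.** Replace the imputation sentence in SAP section 6 with wording such as: *Missing BPI-SF scores will be imputed under a multivariate normal model that contains randomized group (with a separate effect at each visit), BPI-SF scores at all visits, and every control variable in the primary model.* This settles both open points, group and the other visits' scores.

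The cost is one SAP sentence and a few more terms in the imputation code. All the variables are already collected, and the primary analysis does not change.

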#### 4.5 Follow- up procedures (by time points)

Follow-up data will be obtained for subjects in all arms of the study by a RA who is blind to the subject's group allocation. Data collected at all follow-up time points will include a phone interview with the patient and data obtained from the patient's EHR. Prior to each phone interview, data will be extracted from the patient's EHR by an RA using standardized questions with explanations in REDCap.

**1-Week Follow-up:** This call can take place anytime from the 7th day through the 12th day after study enrollment (or hospital discharge if subject was admitted). Following the phone script, the RA will make a total of 10 attempts via phone call, text, or email to reach the subject for the follow-up interview. This phone interview will take ~20 minutes and include the questionnaires noted below. The purpose of this call is to assess the mechanisms that might contribute to patient recovery. However, some outcomes (pain, healthcare use) will also be assessed at this time point.

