## 5.4 Schedule of Events

Procedures	Enrollment / Baseline	Telecare (48-72 hrs after enrollment)	Week 1 Follow-up Call	1, 3, 6, and 12 Month Follow-up Call
Demographics	X			
Obtain verbal informed consent	X			
Randomization	X			
Administer educational video	i, ii			
Call with research nurse		i		
Data Collection Measures/Questions				
Assess access to primary care provider question	X			
Overview of analgesic use (opioid and non-opioid)	X		X	X
Use of other pain management strategies	X		X	X
Brief Pain Inventory-short form (pain severity only)	X			
Brief Pain Inventory-short form (pain severity and pain interference)			X	X
Pain recovery questions	X			
Prior history of chronic pain questions	X			
Pain Catastrophizing Scale-short form	X			
PROMIS Global Health-2a (prior to pain)	X			
PROMIS Physical Function (prior to pain)	X			
PROMIS Global Health-2a (including pain)	X		X	X
PROMIS Physical Function (including pain)	X		X	X
Patient Health Questionnaire (Prior to pain)	X			
Generalized Anxiety Disorder-2 (Prior to pain)	X			
Control Preference Scale	X			
Pain Self-efficacy questionnaire-4 item version	X		X	
Single Item Literacy Screen	X			
Tobacco Screening Measure	X			
Global Impressions of Change			X	X
Preparedness and Confidence questions			X	
Opioid specific questions*	X		X	X
Non-opioid analgesic questions	X		X	X
Analgesic side effects			X	X
Pittsburgh Insomnia Rating Scale			X	X
International Physical Activity Questionnaire			X	
Health Utilization questions*	X		X	X
COVID-19 activity questions				X**

i Subjects in Full intervention arm

ii Subjects in Video-only intervention arm

\*Data obtained through Electronic Health Record AND Questionnaires

\*\* month 3 only

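### The primary model and the planned imputation leave out the 1-week BPI-SF; adding it as a non-tested visit is a cheap way to make missing-at-random more credible

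*SAP*

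**What the plan says.** **Model.** SAP Section 9: "This model will include all pain severity scores (1, 3, 6, and 12 months) as outcomes". The 6-df and 3-df contrasts use months 1, 3 and 6 only, so the 12-month score is carried without being tested. (I read the outcome as the combined severity and interference score of SAP Section 5a. The quoted sentence names severity alone and should be reconciled with that.) Early pain enters through a covariate: "controlling for site type (ED vs. Urgent Care), baseline pain severity".

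**Missing data.** SAP Section 6: "Missing data for the primary outcome will be ignored (treated as missing at random) in the primary ITT analysis". In addition, "outcomes for any visits that fall outside the ± 7 day window will be set to missing for the primary analysis". For the multiple-imputation sensitivity analysis, "imputations will be based on all of the control variables included in the primary model". Week 1 is not mentioned.

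**The 1-week call.** Protocol 4.5 gives its main purpose as mechanisms, but adds that "some outcomes (pain, healthcare use) will also be assessed at this time point". On who collects the data: "Follow-up data will be obtained for subjects in all arms of the study by a RA who is blind". The Schedule of Events (Protocol 5.4) marks both severity and interference at week 1, so the combined score can be computed there. The same schedule marks severity only at baseline, whereas Protocol 5.2 describes the 11-item form at baseline.

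**Timing.** The 1-week window is days 7 to 12 from enrolment, or from hospital discharge for admitted patients. All later windows run from enrolment (Protocol, definitions of time periods).

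**The concern.** A likelihood-based mixed model protects against loss that depends on what the model contains. As written, it contains baseline covariates and scores from month 1 onwards. A participant reached at week 1 and not again contributes no outcome, although a score on the primary scale was recorded. If the schedule is right about baseline, week 1 is also the first measurement of interference, which is half of the primary outcome. The imputation analysis names the same control variables, so as written it does not close the gap.

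At stake is the arm comparison if people with more (or less) pain at week 1 leave at different rates by arm. That is conceivable: the SAP calls the trial open-label, and only the full-intervention arm gets a nurse call. The SAP already carries one non-tested visit, so a second would fit its own approach.

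**Working it through.** **1. Loss implied by the protocol.** Protocol 6.2 assumes exponential loss reaching 20% at 12 months. With 12 months taken as day 360, the rate is −ln(0.8)/360 = 0.000620 per day, and loss by day t is 1 − exp(−0.000620 t):

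| Day | Lost |
|---|---|
| 7 | 0.43% |
| 30 | 1.84% |
| 90 | 5.4% |
| 180 | 10.6% |
| 360 | 20% (the stated figure) |

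Between day 7 and day 30 the loss is 1.84 − 0.43 = 1.4%, about 6 of 400. For these people week 1 would be the only post-baseline score. A further 10.6 − 1.84 = 8.7% leave between day 30 and day 180 and normally already have a 1-month score in the model. Missed or out-of-window 1-month calls would add to the affected share; the documents do not say by how much.

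**2. Assumptions.** The protocol's means and covariance matrix are in figures not shown, and it states no figure for this bias. I assume SD 2.4; correlations 0.6 (week 1–month 1), 0.5 (baseline–week 1) and 0.4 (baseline–month 1), all within 0.3–0.7; and a doubling of dropout risk per SD of 1-week pain, ln 2 = 0.693.

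**3. Bias by hand.** If a fraction p is lost between week 1 and month 1, the baseline-adjusted month-1 mean among those remaining shifts by about

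p/(1 − p) × 0.693 × SD × (0.6 − 0.5 × 0.4)

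- p = 0.014: 0.0142 × 0.693 × 2.4 × 0.40 = 0.009. That is about 0.01 if the dependence is in one arm only, and 0.02 if it runs in opposite directions in the two arms.
- p = 0.10: 0.111 × 0.693 × 2.4 × 0.40 = 0.074, or 0.15 if opposite.
- Same dependence in both arms and no treatment effect: the shifts cancel.

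The formula is a small-loss approximation. Simulation gives 0.01–0.02 at the planned loss and 0.07–0.14 at about 10% missing from month 1.

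**4. Sensitivity.** A wider simulation used SD 2.5, week 1–month 1 correlation 0.5–0.7, odds ratio 1.5–2.5 per SD, and all loss placed between week 1 and month 1:

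| Loss after week 1 | One arm only | Opposite by arm | With week 1 in the model |
|---|---|---|---|
| 1.4% | at most about 0.02 | at most about 0.03 | within 0.01 of zero |
| 10% | 0.02–0.12 | 0.05–0.23 | within 0.01 of zero |
| 20% | 0.04–0.22 | 0.08–0.45 | within 0.01 of zero |

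With the same mechanism in both arms, bias is zero under the null and 0.00–0.06 under a 20% effect. Under the whole planned exponential pattern, with dependence up to 2.5 per SD, the 1–6-month average bias was at most 0.02 (one arm) and 0.04 (opposite).

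**5. Scale.** If usual-care means are 4.0, 3.5 and 3.2 (assumed), the protocol's 20% effect is 0.80, 0.70 and 0.64 points. A bias of 0.01–0.02 is then about 1–3% of it (0.01/0.80 to 0.02/0.64), and 0.07–0.14 is about 9–22% (0.07/0.80 to 0.14/0.64).

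**6. Error rate.** One 3-df test at 2.5%, no true effect, 133 per arm, opposite dependence, odds ratio 2.5, correlation 0.6. Rejection without versus with week 1 was 2.4% v 2.4% at 1.4% loss, 3.9% v 2.8% at 10%, and 8.2% v 2.0% at 20% (3,000 trials each; simulation error about 0.3 points).

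**7. Precision.** At 10% loss with the same mechanism in both arms, the month-1 standard error is 0.306 without and 0.304 with week 1, a variance gain of 1 − (0.304/0.306)² = 1.3%.

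**The case against.** A reader might infer that leaving out week 1 biases the trial. The documents do not support that. No passage shows that loss depends on 1-week pain, still less that it does so differently by arm. Baseline severity is already a covariate, most later leavers have a 1-month score, and at the planned loss the effect is negligible. This stands, and it limits the point to an improvement.

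A reader might also take the imputation to use the control variables and nothing else. The SAP does not say that. A joint normal imputation may also draw on the other visits' scores. What remains is that week 1 is not named.

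It can be argued that the omission is deliberate: the primary outcome is defined at months 1, 3 and 6, and the 1-week call serves the mediation objective. The choice is coherent and no passages conflict. But a mediator role is a reason not to use 1-week pain as a covariate. As an additional outcome visit it does not adjust away any treatment effect, and the estimand and contrasts stay the same.

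Finally, the change is not entirely free. For admitted patients, up to 10% by the protocol's assumption and retained in the ITT population, the 1-week call is timed from discharge. After a long stay it could fall near or inside the day 23–37 window for month 1. This stands and calls for a stated rule.

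**Conclusion.** The point holds as a low-cost improvement. The 1-week combined score is available in all arms, collected blind, and named in neither the primary model nor the imputation. Including it would make missing-at-random more credible.

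The expected gain is small under the protocol's own loss assumption: about 0.01–0.02 points of bias avoided, and then only if dropout depends on 1-week pain differently by arm. It becomes worth having, at about 0.07–0.14 points, if roughly 10% lack usable scores from month 1 on. The variance gain is about 0–2%. The bias figures rest on an assumed SD, correlations and dropout dependence, none of which can be taken from the documents.

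The change does not help with loss before week 1, or with loss that depends on later pain that was never observed.

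**What to change.** - SAP Section 9: add the 1-week BPI-SF combined score as a further repeated outcome with its own visit and arm-by-visit terms. State that the 6-df and 3-df contrasts remain on months 1, 3 and 6.
- SAP Section 6: name the 1-week score as an imputation variable.
- State one rule for admitted patients, for example setting the 1-week score to missing in these analyses if it falls outside days 7–12 from enrolment.

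The cost is SAP wording and no new data. The unstructured covariance grows from 4 × 5/2 = 10 to 5 × 6/2 = 15 parameters, and there are 3 more arm-by-visit means, with 400 participants. The SAP already provides for documented changes decided blind to the true groups. If the primary model is to stay as it is, the same specification can be run as a named sensitivity analysis.
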